6.5. Procedures for registration and randomisation

Eligible patients will be informed about the NeoRad trial before or during NACT. If the patient is interested, the patient will sign an informed consent for the trial provided by the radiooncologist (see also chapter 10.3). Study inclusion must be completed until the evaluation of the first response to the neoadjuvant chemotherapy.

Screening failures have to be documented with reasons.

Definitive study entry is possible after the patient has signed written consent. After a patient has completed the necessary screening visit procedures, the corresponding baseline case report forms (CRFs) have to be completed by the site using the EDC system.

Randomisation and information to the study sites will be performed before first evaluation of response.

The patient insurance policy has to be provided by the participating study site.

In case of unavailability, other technical problems, or questions on the randomisation procedure, please contact

GBG Forschungs GmbH**[name]****[name]****[contact]****[contact]****[contact]****and****[contact]**

6.6 Procedures for handling patients incorrectly enrolled

Patients who are screened but are not randomized should be excluded from the study directly and documented as “screening failure” including the reason for exclusion from the trial.

Patients, who have been randomized in error, despite not meeting all inclusion/ exclusion criteria should be withdrawn from the trial after contacting the Study Chairperson and documentation of the reason for withdrawal (the inclusion/ exclusion criteria are not fulfilled); they will be still included in the ITT analysis up to the timepoint of withdrawal. Patients that fulfill all criteria, have been randomized and are then withdrawn will not be replaced, but the reason for withdrawal has to be documented.

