Sample size and justification	
The primary endpoint of the NeoRad trial is DFS. For sample size calculations, we assumed a 10-year DFS of 70% in the control arm of the trial. This value is based on the experience of the GEPAR trials (GBG data on file, extrapolation from 5years), but takes into account that patients in the NeoRad trial may have a slightly lower risk of recurrence, since some high-risk patients will take part in trials testing novel neoadjuvant treatments and a substantial proportion will receive new postneoadjuvant systemic treatments.
 
Accordingly, we hypothesise that preoperative radiotherapy after NACT will improve 10-year DFS from 70% in control arm to 76.5% in the experimental arm of the trial (HR=0.75), which we consider a clinically relevant improvement.
 
In order to detect a difference of this magnitude at a power of 80%, a recruitment time of 4 years and an additional follow up of at least 6 years, 379 events and a sample size of 1826 patients, 913 in each arm using a 1:1 randomisation, are required to reject the null hypothesis of no improvement on a two-sided type I error level of 0.05. A cumulative drop-out rate of 10% in 10 years is included in these calculations. This calculation is based on an assumed exponential shape of the survival curves and this drop-out process.

Biostatistical methods	
All primary efficacy analyses will follow the ITT principle, i.e. all randomized patients will be included in the analysis and the treatment groups they were randomized to. Time-to-event data, such as DFS and OS, will be displayed by treatment group as Kaplan-Maier curves and compared using the two-sided stratified log-rank test. The

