9.2 Description of analysis sets

9.2.1. Efficacy analysis set

The full analysis set or ITT (intention to treat or “treatment policy”) set will be the primary population for efficacy endpoints, notably for the primary endpoint DFS. For the ITT analysis, all randomized patients will be included as randomized, regardless of possible errors after randomisation.

Patients who have received protocol treatment unless they experience unequivocally documented earlier disease progression and have no major protocol deviations thought to impact the efficacy conclusions of the trial will be included in the per protocol set for the sensitivity analysis of non-inferiority; the final list of the major protocol violations leading to

the exclusion from the per protocol set will be defined in the statistical analysis plan (SAP); patients who were enrolled although they unequivocally did not fulfil the selection criteria of the trial a priori (“non-eligible”) will be excluded from the per protocol set.

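### Section 6.6 stops counting patients randomised in error at their withdrawal, which conflicts with the all-randomised DFS analysis in 9.2.1 and with the data-collection rule in 6.7

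*Protocol*

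**What the plan says.** Protocol 6.6 deals with patients who were randomised "despite not meeting all inclusion/ exclusion criteria should be withdrawn from the trial after contacting the Study Chairperson". For the primary analysis it adds that "they will be still included in the ITT analysis up to the timepoint of withdrawal". The withdrawal is an instruction to the site and does not depend on the patient's wish.

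Three other places bear on the same patients:

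- **Synopsis, biostatistical methods:** "All primary efficacy analyses will follow the ITT principle, i.e. all randomized patients will be included in the analysis".
- **Section 9.2.1:** the ITT set, labelled treatment policy, is the primary population for DFS, and "all randomized patients will be included as randomized, regardless of possible errors after randomisation". The same section deals with ineligibility elsewhere: "patients who were enrolled although they unequivocally did not fulfil the selection criteria of the trial a priori" are the ones who "will be excluded from the per protocol set".
- **Section 6.7:** when a patient withdraws during the trial or follow-up, survival and disease-control data are still to be collected and analysed where possible. Data collection after termination continues unless consent is withdrawn completely.

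Section 9.3.1 censors event-free patients at last contact and treats drop-out as independent right censoring.

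**The concern.** A treatment-policy DFS analysis needs each randomised patient's events up to the end of follow-up. Under 6.6 a patient with an entry breach contributes only until someone notices the breach. Later events either go uncollected or are collected and ignored, depending on whether a site follows 6.6 or 6.7. If they go uncollected, no analysis plan and no pre-analysis meeting can recover them.

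The censoring is tied to patient characteristics. Some breaches, such as another malignancy, plausibly carry a different DFS hazard, so the independence assumed in 9.3.1 need not hold. Eligibility is fixed at baseline and balanced in expectation, but it is discovered after randomisation in an open trial. Exclusion criterion 14 concerns conditions that prohibit neoadjuvant radiotherapy, which only the experimental arm receives, so such a breach may surface more readily there. At stake is mainly the non-inferiority step, which comes first and must succeed in the ITT set before superiority is tested.

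**Working it through.** **Inputs from the protocol (9.3.1, 9.4).** Two-sided alpha 0.05; power 80%; HR 0.75; 10-year DFS 70% and 76.5%; drop-out 10% in 10 years; 4 years' accrual, 10 years in total; 913 per arm; 379 events; non-inferiority margin 1.15.

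**Inputs assumed, because the protocol gives none.** Share randomised in error f = 2% to 5%; withdrawal close to randomisation; hazard of these patients relative to the others k = 1.5 to 3.

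**1. The plan's own figures.** Events = 4(1.96 + 0.8416)² / (ln 0.75)² = 379.4, against 379 stated. The exponential (Lachin-Foulkes) calculation with hazards 0.0268 and 0.0357 and drop-out 0.0105 gives 914 per group, against 913 stated. Both reproduce.

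**2. Expected events.** With hazard l, drop-out hazard d and h = l + d, the event probability is P(l) = (l/h) × [1 − (e^(−6h) − e^(−10h)) / (4h)]. Using unrounded hazards −ln(0.765)/10, −ln(0.70)/10 and −ln(0.90)/10, P is 0.1848 (experimental) and 0.2378 (control). Over 913 per arm this is 168.7 + 217.1 = 385.8 events.

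**3. Power if a share f is lost equally in both arms.** Power = Φ(√E/2 × |ln 0.75| − 1.96).

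| f | patients (1826 × f) | E from 385.8 | power | E from 379 | power |
|---|---|---|---|---|---|
| 0 | 0 | 385.8 | 80.7% | 379 | 80.0% |
| 2% | 37 | 378.1 | 79.9% | 371 | 79.1% |
| 5% | 91 | 366.5 | 78.6% | 360 | 77.9% |

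Between 0 and 5%, the loss is about 2 percentage points on either base.

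**4. Worst-case shift in the hazard ratio.** Suppose the true HR is 1.0 and all such withdrawals occur in the experimental arm. The hazard of the other patients is l = 0.0357 / (1 − f + fk), so that the average hazard stays at 0.0357. The experimental arm then shows rate l. The control arm, which keeps its ineligible patients, shows [(1−f)P(l) + fP(kl)] / [(1−f)P(l)/l + fP(kl)/(kl)]. The apparent HR is the ratio of the two.

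Example with f = 5%, k = 3: l = 0.0357/1.10 = 0.03245; control rate = 0.2341/6.679 = 0.03504; HR = 0.03245/0.03504 = 0.926.

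| f | k = 1.5 | k = 3 |
|---|---|---|
| 2% | 0.991 | 0.970 |
| 5% | 0.977 | 0.926 |

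As a share of the margin on the log scale, ln(HR)/ln(1.15), the shift is about 7% to 22% at f = 2% and 17% to 55% at f = 5%, in favour of the experimental arm. If withdrawal is equal in share and timing by arm, this shift does not arise.

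**The case against.** The strongest reply is that 6.7 already contains the right rule. On that reading 6.6 is loose wording and little is lost in practice. This stands in part. A reader might infer from 6.6 alone that all later events of these patients are certainly lost. The protocol does not settle that, because 6.7 points the other way. But 6.6 is the specific instruction for this group and states an explicit cut-off, so the general text does not override it and sites are left with two rules.

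Second, 6.6 and 9.2.1 agree on membership, since both keep these patients in ITT. The phrase in 9.2.1 about errors also refers to errors after randomisation, whereas an entry breach precedes it. Both points are correct. The conflict lies only in follow-up and events after withdrawal, where the all-randomised, treatment-policy wording still applies.

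Third, a reader might infer that detection of breaches does differ by arm. The documents do not show this. The schedule in Table 3 gives the standard arm sonography at the end of chemotherapy and again before surgery. The re-biopsies in the experimental arm are recommended, not required (6.1). Planning CT is used in both arms, and radiation oncology obtains consent in both. Criterion 14 is the better example, and it shows only a possibility.

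Fourth, two further inferences fail. The analysis is not event-driven: no passage triggers it at 379 events, and the end of follow-up is set by calendar (Q1 2034). Nor is the bias without limit: within the assumed ranges it is bracketed above.

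**Conclusion.** The point holds as a conflict inside the protocol. Section 6.6 ends the ITT contribution of patients randomised in error at a withdrawal they did not ask for, against the synopsis, 9.2.1 and 6.7, and the resulting censoring need not be independent as 9.3.1 assumes.

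Its size rests on an assumed ineligibility rate of 2-5%. The power loss on that basis is minor. A bias of any consequence needs withdrawals concentrated in one arm and a clearly higher hazard among those withdrawn; neither is shown. The one-arm figures are therefore an outer case under the stated assumptions. The point deserves correction because the non-inferiority margin is narrow, uncollected events cannot be recovered later, and the remedy is cheap. It concerns ineligible patients under 6.6 only, and not the separate exclusion in 6.7 for metastasis or patient wish before local therapy.

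**What to change.** Amend 6.6 so that it agrees with 6.7 and 9.2.1. For a patient found after randomisation to breach an entry criterion:

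- record the breach as a protocol deviation;
- continue to collect DFS, OS and recurrence data on the existing visit schedule;
- analyse her in the ITT set, as randomised, for her full follow-up;
- exclude her from the per-protocol set only;
- stop data collection only if she withdraws consent.

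Delete the clause that limits the ITT contribution to the time before withdrawal. The amendment concerns data collection and analysis, and says nothing on how these patients are treated.

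The cost is one paragraph in an amendment and continued follow-up of a small number of patients (37-91 if 2-5% is right). The 1826 patients, 379 events and 80% power are unchanged. The change should be made early, while follow-up of any patient already affected can still be resumed.

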6.7 Termination and interruption

Criteria for exclusion of subjects

Prior to preoperative radiotherapy (experimental arm) or surgery (standard arm), randomized subjects who experience distant metastasis or who wish to withdraw from the study will be excluded. In the present modified intention to treat analysis, all other patients are included in the analysis. The data of the excluded patients should not be obtained within the study. These patients are treated outside the study according to the currently valid guidelines and therapy recommendations and are not included in the analysis. For these patients, it is possible to enroll additional patients in the study. In all other situations, no patient can subsequently replace a patient. If a patient withdraws from the study during the trial or follow-up, survival

and oncological control data should still be gathered and included in the analysis, whenever possible.

Termination

Any decision to terminate an individual patient from a clinical trial must be made by the patient's healthcare team and with consideration of the patient's best interests. However, any discontinuation or interruption of therapy should be avoided whenever possible. The study center is available to the local study site for consultation. Nevertheless, data collection from these patients should continue (except the case when patient withdraws her consent to the study completely) since it can still provide valuable insights into the safety and efficacy of the treatment being studied. In general, patients who were enrolled in a clinical trial will be considered for analyses even if the study protocol including radiotherapy is terminated before completion. However, subgroup analyses are conceivable. Within the framework of this study, a retrospective quality assurance of all patients will be carried out. From the collected data, compliance with the study protocol can be checked at the end of the study. Regardless of compliance with the protocol, the patients are included in the analysis. Regardless of the quality of treatment, all patients will be included in the analysis. In a further analysis, the value of protocol compliance can be investigated.

6.8 Definition of predefined toxicity from radiotherapy and surgical treatment for safety analysis

Every adverse event (AE) after radiotherapy will be coded, categorized and graded in regards of its severity according to v5.0. If an event cannot be categorized it will be captured in a written form and grade as follows:

Grade 1 - low

Event is noticeable but tolerable

Grade 2 - moderate

Event limits everyday life activities

Grade 3 - severe

Event prohibits everyday life activities completely

Grade 4 – life-threatening

Grade 5 - deadly

Event leads to patient's death

Every adverse event has to be evaluated in terms of causalities:

Every adverse event has to be documented regardless of the examining doctor's opinion whether there is a causality to radiotherapy or not.

Adverse events are first recorded before the start of local therapy (after neoadjuvant chemotherapy), then during local therapy and as part of the follow-up examinations .

The following common toxicities are documented as AE of Special Interest as a Grade 3 toxicity or worse: skin reaction, pain and feeling of pressure. Complaints that appear during local examination are also documented as AE: edema of the breast, inflammation, haematoma, seroma and wound healing difficulties. Documentation includes the type of event: beginning, distinctness/ severity.

Signs of illness, symptoms and changes in laboratory values that are causally connected should be summarised to one single disease.

Documentation should be based on the given examination sheets (CRFs). AEs are identified by the doctor and coded by the GBG.

All adverse events that have a connection to the study therapy need to be observed until they disappear or stabilise.

Additional examinations that are deemed necessary by the examining doctor should be documented and marked as such in the CRFs.

[°]III-V Adverse events should be documented within 2 weeks after discovery into the database.

The head of study in Duesseldorf will review the database periodically (minimum 4-week-interval).

A serious adverse event (SAE) in the context of the NeoRad trial refers to any unexpected or significant medical occurrence or outcome that results in one or more of the following:

- 1) Death of a participant

- 2) Life-threatening condition of a participant
- 3) Hospitalization or prolongation of existing hospitalization of a participant (exception: re-resection due to R1-status)
- 4) Disability or permanent damage to a participant

SAEs that have occurred from the initiation of radiotherapy and up to 3 months after radiotherapy should be reported to the GBG on the corresponding form. The GBG will inform the study chairmen. At regular intervals, the SAEs that have occurred will be discussed by the Safety Board of the study. In addition, the heads of study will consider preventive or corrective measures if necessary.

A patient that gets pregnant during study treatment will be withdrawn from the study and documented as drop-out. It is necessary to report to the study centre by sending in the case report. Local documents such as but not limited to hospitalization reports, autopsy reports, pathology report and lab sheets shall be provided in pseudonymized format when requested. Furthermore, the patient will be monitored during her pregnancy and after delivery. The constitutions of both mother and child need to be documented even if deemed normal and if no adverse events occurred.

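### Section 6.7 removes randomised patients with early distant metastasis or withdrawal from data collection and analysis, against the all-randomised ITT primary analysis

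*Protocol*

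**What the plan says.** Section 6.7 sets a rule for the period between randomisation and the first local treatment, which is preoperative radiotherapy in the experimental arm and surgery in the standard arm. In that period "randomized subjects who experience distant metastasis or who wish to withdraw from the study will be excluded". The section continues: "In the present modified intention to treat analysis, all other patients are included in the analysis". For those removed it instructs: "The data of the excluded patients should not be obtained within the study". It also allows them to be made up: "For these patients, it is possible to enroll additional patients in the study".

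Other parts of the protocol say the opposite:

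- Synopsis, Biostatistical methods: "all randomized patients will be included in the analysis and the treatment groups they were randomized to".
- Section 9.2.1, on the ITT set that is primary for DFS: "all randomized patients will be included as randomized, regardless of possible errors after randomisation". Section 9.3.1 repeats the ITT (treatment policy) principle and censors drop-outs. Section 9 nowhere mentions a modified ITT set.
- Section 6.6: eligible patients who "have been randomized and are then withdrawn will not be replaced". Even patients randomised in error are kept in the ITT analysis up to withdrawal.
- Section 6.7 itself: for patients who withdraw during the trial or follow-up, survival and "oncological control data should still be gathered and included in the analysis, whenever possible". Under Termination it says that data collection goes on unless consent is withdrawn completely, and that all patients are analysed whatever the quality of their treatment.

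**The concern.** DFS is counted from randomisation. Distant recurrence is one of its events (section 9.3.1), and Table 1 in section 3.1 lists any distant metastatic disease as an event. A randomised patient whose metastasis appears before local therapy has therefore had a primary-endpoint event, and section 6.7 takes both the patient and the event out of the trial.

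Three features make this more than a wording slip:

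- **The window is real.** Randomisation must precede the first response assessment, so much of the neoadjuvant chemotherapy can lie inside it.
- **Allocation is open.** A patient who does not want her assigned sequence can withdraw, disappear from the analysis and have another patient enrolled for her. ITT exists to prevent this kind of selective loss. The window also closes at a different procedure in each arm, so balance cannot be taken for granted.
- **The instruction acts at the sites now.** An analysis plan can redefine a set later, but it cannot supply outcomes that nobody recorded.

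The primary decision begins with a non-inferiority test of the DFS hazard ratio against 1.15, and that test is sensitive to a small net imbalance in removed events.

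**Working it through.** **Inputs from the protocol (section 9.4, margin from 9.3.1).** 10-year DFS 70% in the control arm and 76.5% in the experimental arm; drop-out 10% in 10 years; accrual 4 years; maximum follow-up 10 years; 913 patients per arm; margin HR 1.15; two-sided 95% CI.

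**Design figure reproduced.** Events = 4 × (1.96 + 0.8416)² / (ln 0.75)² = 379.4, against the stated 379. The planned size rests on all randomised patients and needs no change.

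**Expected events per arm.**

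- Control hazard l = −ln(0.70)/10 = 0.03567 per year; drop-out hazard d = −ln(0.90)/10 = 0.01054; s = l + d = 0.04620.
- P(event) = (l/s) × [1 − (exp(−6s) − exp(−10s))/(4s)] = 0.7720 × [1 − (0.7579 − 0.6300)/0.1848] = 0.2378.
- Control arm: 0.2378 × 913 = 217.1 events. Experimental arm: 217.1 at HR 1, and 244.6 at HR 1.15 by the same formula with hazard 1.15 × l.

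**How many events the window can hold.** The protocol gives no length for it; 3 to 6 months is my assumption.

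- 3 months: 1 − exp(−0.03567 × 0.25) = 0.9%, or 8.1 of 913.
- 6 months: 1 − exp(−0.03567 × 0.5) = 1.8%, or 16.1 of 913.

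These are DFS events of all types at the control hazard. Distant metastases are only a part of them.

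**Effect of removing events.** With kE and kC events removed from the experimental (eE) and control (eC) totals:

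- HR' = HR × (eE − kE)/eE × eC/(eC − kC)
- SE = sqrt(1/(eE − kE) + 1/(eC − kC))
- P(non-inferiority) = Φ((ln 1.15 − ln HR')/SE − 1.96)

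Worked case: true HR 1.15, with 0.5% of 913 = 4.6 events removed from the experimental arm only. HR' = 1.15 × 240.1/244.6 = 1.129 and SE = 0.0937, so P = Φ(0.0188/0.0937 − 1.96) = Φ(−1.76) = 3.9%.

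| Removal | True HR | HR' | P(non-inferiority) |
|---|---|---|---|
| none | 1.15 | 1.150 | 2.5% |
| 1% from both arms | 1.15 | 1.156 | 2.2% |
| 0.5% (4.6 events), experimental only | 1.15 | 1.129 | 3.9% |
| 1% (9.1), experimental only | 1.15 | 1.107 | 6.0% |
| 2% (18.3), experimental only | 1.15 | 1.064 | 12.6% |
| none | 1.00 | 1.000 | 31% |
| 0.5%, control only | 1.00 | 1.021 | 23% |
| 1%, control only | 1.00 | 1.044 | 17% |
| 2%, control only | 1.00 | 1.092 | 8% |

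The 1% one-arm rows are close to the worst case: 9.1 net events exceeds the whole 3-month count of 8.1 and is more than half of the 6-month count. The 2% rows exceed even the 6-month count and mark an extreme.

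**Power.** At the design hazards the window holds about 14 (3 months) to 28 (6 months) DFS events over both arms. If all were lost and not made up, superiority power would be Φ(0.2877 × sqrt(365/4) − 1.96) = 0.785 to Φ(0.2877 × sqrt(351/4) − 1.96) = 0.769, against 0.80. Loss of power is the smaller problem.

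**The case against.** The strongest reply is that the statistics chapter governs. Section 9 names ITT as primary and never uses the term modified ITT, and section 9.6 sends doubtful allocations to a blinded pre-analysis meeting. This does not rescue the plan. Section 6.7 describes the modified set as the trial's present analysis, and its instruction not to collect data takes effect before any such meeting.

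The internal conflict can be softened by reading section 6.7 as a rule with an exception: early exclusions first, then later withdrawals. But withdrawal during the trial literally includes the early window, and the sentences on continued data collection and on analysing all patients remain. The clash with section 6.6 is secondary; it concerns replacement and needs only reconciling.

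On balance between arms, the reply has weight. Both arms receive the same systemic treatment until local therapy, and Tables 3 and 4 schedule CT and bone-scan staging only at baseline in each. No systematic difference in early metastases is shown, and equal removal is slightly conservative for non-inferiority.

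The calculation also treats every removal as an event. A patient who withdraws consent completely at an early date would be censored early under ITT anyway, so removing her changes little. The quantified harm comes mainly from deleted metastases.

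**Conclusion.** The concern holds. The protocol gives two incompatible rules for who is in the primary DFS analysis, and one of them removes primary-endpoint events and stops their collection after open allocation.

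The size is an illustration only. It rests on exponential hazards, an assumed window of 3 to 6 months and an assumed imbalance, since the protocol states no excluded share. With balanced loss the effect is negligible. With a net loss of about 5 events from one arm, false non-inferiority rises from 2.5% to 3.9%, or the chance of showing non-inferiority at a true HR of 1 falls from 31% to 23%. The larger one-arm figures are near or beyond the worst case. Direction is not established.

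This must be fixed because it concerns the primary analysis set and because data not collected may not be recoverable; the case does not depend on any one error rate.

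**What to change.** Amend section 6.7 as follows:

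- Delete the exclusion from analysis, the modified ITT wording, the instruction not to obtain data and the option to enrol additional patients. Reconcile the section with 6.6, 9.2.1, 9.3.1 and the synopsis.
- State that every randomised patient stays in the ITT set and is followed for DFS and survival unless she withdraws consent to data collection, in which case she is censored at that date.
- State that distant metastasis at any time after randomisation counts as a DFS event, in line with Table 1 in section 3.1.
- If a set without early metastases is wanted, define it as a labelled sensitivity analysis.

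If any patients have already been excluded under this rule, resume their follow-up as far as their consent allows.

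The cost is amendment wording and follow-up of a small number of patients who are already randomised. There is no extra recruitment, the sample size stands, and clinical management of these patients need not change.
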